2.2.1 Subgroup of interest

The primary and secondary efficacy endpoints, safety endpoints (adverse events, clinical laboratory values, vital signs, and anti-AMG 334 antibodies), as well as the demographics and baseline characteristics, and the prior migraine prophylactic medication usage information will be analyzed for Chinese subgroup (recruited from China mainland and 3 qualified sites from Taiwan). This is to evaluate the consistency of efficacy and safety effects in Chinese population vs overall population.

In addition, the effect in the following subgroup analysis by baseline characteristic will be investigated with respect to the primary and secondary efficacy analyses as well:

- Prior prophylactic migraine medication treatment failure (Yes or No)
- Medication overuse at Baseline: Yes, No

- Baseline MMD (< median vs \geq median)
- Disease duration (< median vs \geq median)
- Age (< median vs \geq median)
- BMI (< median vs \geq median)
- Sex (Male vs Female)
- Region

The impact of other baseline variables, may be investigated with respect to the primary and secondary efficacy analyses if, upon clinical review, differences between treatment groups are deemed clinically meaningful.

The purpose of the subgroup analyses is to explore if the treatment effect varies across subgroups of interest. Subgroup analyses are performed for primary and secondary efficacy endpoints using the same method as primary analysis method but performed within each subgroup of interest. The treatment difference (or odds ratio) with associated 95% confidence intervals and p-values will be reported within each subgroup.

Note: if the subgroup is the stratification factor (Prior prophylactic migraine medication treatment failure) then it will not be included in the model.

The heterogeneity of the treatment effect across the subgroups will be evaluated for the primary and secondary endpoints by examining the treatment by subgroup interaction and the p-value for the interaction term will be reported. For continuous endpoints, the primary analysis model with the addition of subgroup and treatment group by subgroup interaction as two additional effects will be used. For endpoint based on proportions, a logistic regression model that includes treatment group, stratification factors, baseline value, subgroup and treatment group by subgroup interaction will be used.

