If the value of the group variable cannot be determined, the subject will be excluded from the corresponding subgroup analysis. For each subgroup analysis, if, in any treatment group, the number of subjects is less than 10 for a subgroup, then only summary statistics will be performed.

The adjusted mean changes from baseline, SE's, and 95% CIs for each subgroup and the nominal p-value for subgroup by treatment interaction will be calculated.

The outcome will be displayed in separate forest plot for each endpoint with the following information:

- The number of patients within each subgroup level / treatment arm
- Supporting information such as least squares mean by treatment and subgroup level
- The treatment effect (erenumab 70mg vs. placebo) estimate and two-sided 95% confidence interval within each subgroup level (using the BY statement for the primary analysis model).
- The directions which favor placebo or AMG 334 will be indicated.
- p-value for the treatment*subgroup interaction term.

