2.5 Analysis of the primary objective

2.5.1 Primary endpoint

The primary efficacy variable is the change from baseline in monthly migraine days in the last 4 weeks of the 12-week treatment period.

Analysis of the primary endpoint will utilize the FAS. Subjects will be analyzed according to their randomized treatment group regardless of the actual treatment received during the study.

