2.5.2 Statistical hypothesis, model, and method of analysis

The primary endpoint of the study will be tested for erenumab 70 mg compared to placebo.

Null hypothesis: There is no difference between erenumab 70 mg group and placebo group, in terms of change from baseline in monthly migraine days in the last 4 weeks of the 12-week treatment period.

Alternative hypothesis: There is a difference between erenumab 70 mg group and placebo group, in terms of change from baseline in monthly migraine days in the last 4 weeks of the 12-week treatment period.

The null hypothesis will be rejected if the observed p-value for the between-group comparison is less than the significant level adjusted according to the alpha spending function with the

O'Brien-Flemming approach. The nominal p-value threshold will be calculated upon the exact information collected in the interim analysis, considering the alpha-level spent at interim analysis and considering the actual correlation among the test statistics, in order to achieve a cumulative type I error smaller than the desired significance level (i.e. smaller than the 5% for a two-sided test).

The primary efficacy endpoint variable will be analyzed using a linear mixed effects repeated measures model based on observed monthly data during treatment period, with treatment, scheduled visit, treatment by visit interaction, and the stratification factors and baseline values as covariates. If applicable, unstructured covariance structure is assumed. Least squares means (LSMs) for treatment groups and its associated 95% confidence intervals, difference of LSMs compared to placebo group and the associated 95% confidence interval of the difference, as well as the nominal two-sided p-values, will be tabulated by visit and treatment.

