2.5.4 Sensitivity analyses

Multiple imputation (MI) techniques applying missing at random (MAR) and missing not at random (MNAR) approaches will be used to assess the impact of missing values on the interpretation of the results during study. In addition, the baseline observations carried forward (BOCF) method will also be used. After imputation, the primary efficacy variable at week 12 will be analyzed using an analysis of covariance (ANCOVA) model including treatment group and stratification factor as fixed effects in the model with baseline value as covariate.

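### For the continuous endpoints, the subgroup interaction p-value is a weighted average over Weeks 4, 8 and 12, not a test at the last-4-week endpoint it is printed beside

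*SAP*

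**What the plan says.** SAP 2.5.1 defines the primary variable as the "change from baseline in monthly migraine days in the last 4 weeks of the 12-week treatment period". SAP 2.6.1 places the two continuous secondary endpoints, mMIDAS and acute headache medication days, in the same window.

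SAP 2.5.2 analyses the primary variable with a repeated-measures model on the observed monthly data, "with treatment, scheduled visit, treatment by visit interaction, and the stratification factors and baseline values as covariates", and an unstructured covariance if applicable. SAP 2.6.2 uses a similar model for the continuous secondary endpoints.

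For heterogeneity in these endpoints, SAP 2.2.1 states that "the primary analysis model with the addition of subgroup and treatment group by subgroup interaction as two additional effects will be used". It adds that "the nominal p-value for subgroup by treatment interaction will be calculated" and puts the interaction p-value on a forest plot for each endpoint. The treatment effects on that plot come from fitting the primary model separately within each subgroup level. The subgroup analyses are described as exploratory.

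The responder endpoint is handled differently: "For endpoint based on proportions, a logistic regression model that includes treatment group, stratification factors, baseline value, subgroup" and the interaction. That model has no visit dimension, so the point does not apply to it.

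**The concern.** The primary model includes treatment-by-visit, so it lets the treatment effect change over time. The interaction model adds no subgroup-by-visit and no treatment-by-subgroup-by-visit term, so it forces the subgroup difference in that effect to be equal at Weeks 4, 8 and 12. The separate fits behind the plotted effects make no such restriction. The forest plot for a last-4-week endpoint can therefore pair effects read at Week 12 with a p-value for a different quantity.

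Heterogeneity that emerges by Week 12 would be diluted. Heterogeneity present early and gone by Week 12 could be reported as if it applied to the endpoint. This is the only heterogeneity test on the plot, and it is repeated over eight listed baseline factors. Where the SAP wants Week 12 alone, it says so: in the imputation analyses of SAP 2.5.4, "the primary efficacy variable at week 12 will be analyzed using an analysis of covariance (ANCOVA) model". No equivalent statement covers the interaction. SAP 2.6.2 refers to Section 5.4 for the model descriptions, but that section covers exclusions from analysis sets.

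**Working it through.** **Inputs from the documents** (SAP section 3, Protocol 12.8.1): effect 2.0 days, SD 6.8, 550 subjects including 10% dropout, 1:1 allocation, two-sided 0.05.

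**The plan's own figure.** n per arm = 2 × 6.8² × (1.960 + 1.282)² / 2.0² = 243, so 486 in total, and 486/0.9 = 540 against the stated 550. With 550 × 0.9 = 495 evaluable, the standard error is 6.8 × √(2/247.5) = 0.611 and power is Φ(2/0.611 − 1.96) = 0.905, against the stated 90%. The inputs are sound. The documents give no figure for the interaction test.

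**Assumptions.** The documents give no visit covariance, so I use a range: the same correlation r between any two visits, 0.6 or 0.75, with SD either 6.8 at every visit or rising 5.5/6.2/6.8. Data are complete.

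**Formulas.** Let d be the interactions at Weeks 4, 8 and 12, Σ the visit covariance, and V = Σ × c, where c is the sum of 1/n over the four treatment-by-subgroup cells.

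- SAP term: estimate w′d, with w = V⁻¹1 / (1′V⁻¹1) and SE = (1′V⁻¹1)^(−1/2).
- Week 12 contrast from the model with the visit interactions: estimate d₁₂, with SE = 6.8 × √c.
- Rejection probability at nominal 5%: Φ(m/SE − 1.96) + Φ(−m/SE − 1.96), where m is the estimate.

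**Equal subgroups (50:50).** c = 4/(495/4) = 0.0323, and the Week 12 SE is 6.8 × √0.0323 = 1.22.

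| SD over visits | r | Weights Wk 4/8/12 | SE | 0/1/2 | 2/1/0 | 2/2/2 |
|---|---|---|---|---|---|---|
| equal | 0.6 | .33/.33/.33 | 1.05 | 15.9% | 15.9% | 48.0% |
| equal | 0.75 | .33/.33/.33 | 1.12 | 14.6% | 14.6% | 43.3% |
| rising | 0.6 | .58/.29/.13 | 0.92 | 9.2% | 34.8% | 58.2% |
| rising | 0.75 | .73/.27/.00 | 0.97 | 5.9% | 43.3% | 54.2% |
| Week 12 contrast | any | 0/0/1 | 1.22 | 37.3% | 5.0% | 37.3% |

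The last three columns give the probability of rejection for interactions of that many days at Weeks 4/8/12. For 0/1/2 the SAP term estimates 0.3 to 1.0 days instead of 2.0. In the last rising-SD row, Week 12 carries essentially no weight.

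**Unequal subgroups (20:80).** c = 2/49.5 + 2/198 = 0.0505, and the Week 12 SE is 1.53. The SAP term against the Week 12 contrast gives 5.6% to 11.9% against 25.8% for 0/1/2, 11.1% to 29.9% against 5.0% for 2/1/0, and 30.0% to 41.0% against 25.8% for 2/2/2.

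**Simulation check** (4000 runs, 124 per cell, unstructured covariance estimated; SAP term against Week 12 contrast):

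- Equal SD, r = 0.6: 15.7% v 36.8% (0/1/2), 16.6% v 5.0% (2/1/0), 47.2% v 35.0% (2/2/2).
- Rising SD, r = 0.75: 6.3% v 37.4%, 44.8% v 5.7%, 53.8% v 37.0%.

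These agree with the formulas.

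**The case against.** Nothing in the plan rests on this p-value. It is nominal and exploratory, and the primary test, the interim decision and the China effect-ratio criterion do not use it. The subgroup estimates and intervals stay visible on the same plot. All of that stands, and it limits the consequence.

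The shared term is also a valid 5% test of no interaction at any visit, and the more powerful one when heterogeneity is stable. That is correct. The 15% to 43% under 2/1/0 is therefore not type I error inflation: there is real heterogeneity at Weeks 4 and 8, and the term finds it. The trouble is only that the result is attached to the last 4 weeks.

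The scenarios are strong ones. With milder drift in the 50:50 case, 1/1.5/2 days gives 22% to 30% against 37%, and 1.5/1.8/2 gives 35% to 43% against 37%, which is about break-even. A 2-day interaction equals the whole assumed treatment effect, and even then the Week 12 contrast has only 37% power. The extreme figures need both rising SDs and r = 0.75, and all figures are for migraine days. This shows that the cost shrinks as the interaction nears constancy, but it does not change what the p-value tests.

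Finally, the output shells and code cannot be seen, and a visit-specific contrast may be specified there. The SAP sentence as written does not ask for one.

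**Conclusion.** The concern holds for the three continuous endpoints. Followed as written, SAP 2.2.1 yields a p-value for a covariance-weighted average of the interactions at Weeks 4, 8 and 12. Constancy over visits guarantees that this equals the Week 12 interaction; otherwise the two agree only by coincidence. In the 50:50 case the mismatch costs up to about 31 percentage points of power (37.3 − 5.9) for an interaction that grows to 2 days at Week 12. It adds up to about 38 points of flagging (43.3 − 5.0) for one that has gone by then. Those sizes rest on the assumed covariance and interaction patterns; the mismatch itself follows from the model terms alone. The harm is a heterogeneity p-value that can disagree in either direction with the effects beside it. It should be corrected, but it does not threaten the trial's main conclusion.

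**What to change.** For the continuous endpoints, add subgroup-by-visit and treatment-by-subgroup-by-visit to the interaction model in SAP 2.2.1. Report the Week 12 treatment-by-subgroup contrast p-value on the forest plot, state that the plotted effects are for Week 12, and keep the visit-averaged test as a labelled secondary line. If the shared term is preferred for power, state the constancy assumption and label the p-value as averaged over Weeks 4, 8 and 12. Settle the choice before unblinding.

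The cost is two model terms and one contrast on data already collected. There are two limits. If the interaction really is constant, the Week 12 contrast has less power (37% against 43% to 58% in the 50:50 case), which is a reason to keep the averaged line. The change also aligns only the time point: the pooled model still shares covariance and covariate effects across subgroups, which the separate fits do not.

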2.3 Subject disposition, demographics and other baseline characteristics

2.3.1 Subject disposition

Randomized

Subjects are considered randomized if they have been assigned a randomization number.

Exposed to Investigational Product

Subjects are defined as being exposed to IP if they receive at least one dose of IP.

Completing the DB Treatment

Subjects are defined as completing the treatment period if they receive the week 8 IP dose. It will be derived from Treatment Disposition Form with “Completed” as subject status.

Completing the DB period

Subjects are defined as completing the DB period if they complete all visits up to EOT assessments at Week 12.

Entering into the OLE Period

Subjects are considered entering into OLE period if they complete the DB period and sign on ICF for OLE period.

Completing the Study

Subjects are defined as completing DB period if they complete the safety follow-up visit (week 20), or continue with OLE treatment until the end of study. It will be derived from Study Disposition Form with “Completed” as subject status.

Subject disposition for DB period will be displayed by randomized treatment and overall on FAS, in terms of:

- the number and percentage (based on the number of subjects within each randomized treatment arm) of subjects who complete the DB treatment, or discontinue the DB treatment prematurely along with the primary reason
- the number and percentage of subjects who has completed DB period and enter into OLE period or safety follow-up visit
- the number and proportion of subjects, who complete the DB period, or discontinue the DB period prematurely along with the primary reason for study

The subject disposition for OLE period will be summarized on OAS, in terms of:

- the number and percentage of subjects who complete the OLE treatment, or discontinue the OLE treatment prematurely along with the primary reason
- the number and percentage of subjects who complete the OLE period, or discontinue the OLE period prematurely along with the primary reason

In addition, the total number of subjects screened and the number of subjects screened, but not randomized (discontinued prior to screening phase completion or prior to baseline period completion) will be summarized, including the reason for non-inclusion into the study.

The number of subjects within each of the analysis sets used in the study will be given.

The number of subjects with PDs according to the applicable SOP will be presented for DB Period. The results of the PDs will be grouped using the broad categories defined in the applicable SOP, which currently are:

- Eligibility: Subject did not satisfy entry criteria
- Withdrawal: Subject developed study/treatment withdrawal criteria during the study, but was not withdrawn
- Study Drug: Subject received the wrong treatment or incorrect dose
- Concomitant Medication: Subject took a prohibited concomitant medication
- Other GCP deviation

A complete list of the PDs can be found in the Edit Check Specifications document in CREDI.

Subjects with PDs and non-PDs leading to data exclusion from analysis sets will be listed.

To evaluate the impact of COVID-19 on trial integrity, the number of subjects randomized during COVID-19 pandemic period, the number of subjects under DB period during COVID-19 pandemic, as well as the number of subjects who reported COVID-19 related PDs during DB period will be summarized.

The COVID-19 related PDs will be grouped in summary by following categories which was defined by clinical trial team with reference to COVID-19 guidance released by Novartis:

- Missed visit due to COVID-19
- Visit done outside of study site due to COVID-19
- Assessment/procedure changed due to COVID-19
- Non-compliance with baseline period duration due to COVID-19
- Non-compliance with no re-screening post-baseline failure due to COVID-19
- Discontinuation due to COVID-19
- Treatment not given or delayed due to COVID-19
- Changes in drug supply method (self-administration) due to COVID-19

2.3.2 Demographic variables and other baseline characteristics

Demographic variables and other baseline characteristics including previous migraine treatments will be summarized for each randomized treatment group and for all subjects (total) using FAS.

At baseline (end of the baseline period; see [Section 2.1.1.2](#), baseline definition), the following demographic and baseline characteristics will be summarized:

- Categorical variables:
 - Sex
 - Ethnicity
 - Race
 - Acute headache medication (yes, none) during baseline period
 - Strata*: Prior prophylactic migraine medication treatment failure (prior prophylactic migraine treatment failure, due to efficacy or tolerability, vs no prior prophylactic migraine treatment failure).
 - Strata*: Medication overuse at Baseline (yes, vs no)
 - The number of prior prophylactic migraine treatment category (by counting the category defined in section 2.1.2)
 - The number of prior prophylactic migraine treatment failure (by counting the category defined in section 2.1.2)
 - Aura status during baseline: Migraine with aura (ever experienced a migraine with aura during the baseline period), migraine without aura (never experienced any migraine with aura during the baseline period)
 - Beck Depression Inventory (BDI)-II total score severity grade (minimal depression (0-13), mild depression (14-19), moderate depression (20-28))
- Continuous variables:
 - Age
 - Height (cm)
 - Weight (kg)
 - Body Mass Index (BMI, kg/m²)
 - Age at onset of migraine (years)
 - Disease duration of migraine with or without aura (years)
 - Monthly migraine days during baseline period
 - Monthly acute headache medication days during baseline period

*value used for randomization.

Descriptive statistics (mean, median, standard deviation, minimum, and maximum) will be presented for continuous variables for each randomized treatment group and for all subjects (total) using FAS. The number and percentage of subjects in each category will be presented for categorical variables for each treatment group and all subjects (total).

If multiple races have been reported for a subject, the subject will be categorized as multiple races and in each selected race category.

To evaluate the impact of COVID-19 on study population, the demographic and baseline characteristics will be summarized in the same manner, respectively for subjects who are randomized pre-COVID-19, and subjects who are randomized during COVID-19.

The number of subjects per country for each treatment group will be presented.

Summary of prior migraine prophylactic treatment and reasons for discontinuation will be presented by treatment group and by medication category (as defined in [section 2.1.2](#)).

Subject demographics and baseline characteristics including stratification factors, ethnicity and child bearing status will be listed by treatment.

Subject disease history characteristics (listed below) collected on the “Headache and Migraine Frequency History” CRF page will be listed by treatment:

- Age at onset of migraine (years)
- Disease duration of migraine with or without aura (years) – derived.
- Frequency of migraines over the past 3 months (average days per month subject had migraines)
- Frequency of headache (migraine and non-migraine) over the past 3 months (average days per month subject had headache)

2.3.3 Medical history

Relevant medical history/current medical conditions present before signing the Informed consent will be recorded on the ‘Medical History’ CRF page.

Any condition entered will be coded using the latest version Medical Dictionary for Regulatory Activities (MedDRA) prior to database lock and summarized by primary system organ class (SOC) and preferred term (PT) for each randomized treatment group and for all subjects (total) using FAS (randomized analysis set). The SOCs will be presented in alphabetical order. Preferred terms will be ordered within each SOC by decreasing order of frequency in the AMG334 70 mg arm.

Relevant medical history and current medical conditions will be listed by treatment.

2.4 Treatments (study treatment, rescue medication, concomitant therapies, compliance)

2.4.1 Study treatment / compliance

Exposure will be calculated for subjects in the SAF and is defined as the number of investigational product injections received (planned to be 1 injection per dose) by subject.

Descriptive statistics will be produced to describe the exposure to investigational product by treatment group. The proportion of subjects who received 1, 2 or 3 injections will be provided.

The duration of exposure since first injection will be summarized descriptively by treatment group.

At each visit, the number and percentage of subjects receiving an investigational drug (AMG 334 or placebo) dose will be summarized by treatment group. Additionally, the number and percentage of subjects with dose change and reason for dose change will be summarized by treatment group and by visit.

2.4.2 Prior, concomitant and post therapies

The number and percentage of subjects receiving concomitant medications, and significant non-drug therapy will be summarized by SOC, preferred term (coded by WHO Anatomic Therapeutic Chemical classification [ATC]) and by treatment arm, and be listed.

Use of other non-pharmacological treatments and traditional techniques (such as acupuncture, traditional and herbal medicine) during the baseline period and the treatment period will be summarized by category of medication for each treatment group in a separate table.

Use of acute headache medication during the baseline period and the treatment period will be summarized by category of medication for each treatment group.

